17.2 SAFETY AND OTHER EVALUATIONS

This section specifies analyses related to COVID-19 pandemic from the following aspects:

- Disposition
- Study visit (missing entire visit due to COVID-19 or missing assessments due to COVID-19)
- Protocol deviation
- Study drug disruption due to COVID-19

- TEAEs related with COVID-19 and supplemental signs and symptoms
- COVID-19 status (COVID-19 testing results or contact with a COVID-19 positive person)

OL Safety Population or DB Safety Population will be used for the planned analyses described above. The number of participants impacted by COVID-19 during the OLTP will be summarized overall and the number of participants impacted by COVID-19 during the DBTP will be summarized by treatment group and overall. In addition, the number of patients impacted by COVID-19 and their corresponding disposition status in the OLTP and DBTP will be summarized respectively.

The number of patients who missed at least one entire visit due to COVID-19 will be summarized overall for the OLTP and by treatment group and overall for the DBTP. Furthermore, the number of patients who missed at least one assessment due to COVID-19 will be summarized by assessment category (laboratory, C-SSRS, urine pregnancy test, vital signs, ECG, and ophthalmological assessments) and overall. Similar summaries will be provided by visit.

The number of patients with significant protocol deviation due to COVID-19 will be provided. The number of patients with study drug disruption due to COVID-19 will be provided as well. The number of participants with TEAEs related to coronavirus infection or coronavirus test positive will be provided. Supporting listings for the described analyses above will also be provided.

18.0**CHANGES TO ANALYSES SPECIFIED IN PROTOCOL**

1. The definition of the DB ITT population in this document Section 6.7 was updated and overwrites the one specified in the Protocol Amendment 5, and reads as follows:

The DB ITT Population will consist of all who took at least 1 dose of DB IP and had at least 1 post-randomization assessment of the YMRS, MADRS, or CGI-S scores during the DBTP of the study, or had a relapse event.

2. The cutoff for the Age group in the SAP Section 7.4 was updated from 55 to 45 years old, due to imbalance between <55 and >=55 years based on the blinded data review. Now it reads as:

- Age group (< 45 years, \geq 45 years).

APPENDIX I. SAS PROGRAM FOR PRIMARY EFFICACY ANALYSIS

The primary efficacy analysis for time to relapse include (1) the log-rank test and (2) the Cox proportional hazards model with treatment group and modified index episode (manic or depressive) as the covariate. The sample SAS code for these analyses are provided below. Note in the dataset adtte (DB ITT population), variables trt02pn and trt02p are for the double-blind treatment group, episode is for the modified index episode, aval is for the time (days) to censor/relapse, and cnsr is for the status of censored (=0) or relapsed (=1).

(1) SAS program for log-rank test comparing treatment groups trt02pn=0 and =1:

```
proc lifetest data=adtte method=km;
  strata episode region/test=logrank group=trt02p diff=control('Placebo');
  time aval * cnsr(0);
run;
```

(2) SAS program for Cox proportional hazard model:

```
proc phreg data=adtte;
  class trt02p (ref= 'Placebo') episode(ref='depressive') region;
  model aval * cnsr(0)= episode region trt02p/rl;
  contrast ' cariprazine 1.5 mg/d vs placebo Episode=depressive'    trt02p 1 0  episode 0/
estimate=exp e;
  contrast ' cariprazine 3.0 mg/d vs placebo Episode=depressive'    trt02p 0 1  episode 0/
estimate=exp e;
  contrast ' cariprazine 1.5 mg/d vs placebo Episode=manic'      trt02p 1 0  episode 1/ estimate=exp e;
  contrast ' cariprazine 3.0 mg/d vs placebo Episode=manic'      trt02p 0 1  episode 1/ estimate=exp e;
  ods output parameterestimates=pvval;
run;
```

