proc sort data=a1 out=a2;
  by randdt;
run;

data b2;
  set a2 end=eof;
  retain franddt;
  format franddt yymmdd10.;
  if _n_=1 then do;
    franddt = randdt;
    set b1;
  end;
  if eof then do;
    lranddt = randdt;
    ta = lranddt - franddt; * duration of enrollment period;
    tfmin = %eval(&fllow.*7);
    tfmax = %eval(&fhigh.*7);
    output;
  end;
  keep franddt ta tfmin tfmax;
  label franddt="Randomization Date for First Randomized Subject"
    ta="Duration of Enrollment Period (days)"
    tfmin="Minimum Follow-up Time (days)"
    tfmax="Maximum Follow-up Time (days)";
run;

proc print data=b2 label;
  var franddt ta tfmin tfmax;
run;

data a3;
  set a1;
  if _n_=1 then set b2;
  e = randdt - franddt; * enrollment time for the current subject;
  *if compynfl="Y" or index(upcase(trmspc),"26 WEEK")>0 then do; /* completed the study */
  if compdbfl="Y" then do;
    tf = durdb;
    complete=1;
  end;
  else do; * relapsed or discontinued for other reasons;
    tf = min(ta - e + tfmin, tfmax);
    complete=0;
  end;
run;

data raw1;
  merge a3
    ad.adtte(keep=aval cnsr paramn subjid trt03pn where=(paramn=0)); ***paramn=0 corresponds
  to time to relapse***;
  by subjid;
  status=(cnsr=0);
  rename subjid=subj trt03pn=treated aval=time tf=followup;
  keep subjid trt03pn cnsr status aval complete tf episode;
run;

* check number of events per treatment group;
proc freq data=raw1;
  tables treated*status/norow nocol nopercents;
run;

ods listing close;

* examine Bayesian analysis results to determine thinning;
proc phreg data=raw1;
  class episode;
  model time*status(0)=episode region treated;
  bayes piecewise=hazard;
run;

* ==> thin=10 is enough to achieve approx. indep. posterior samples;
%let thin=10; * thinning;
%let ninterval=8; * number of time intervals for piecewise exponential;
%let nimps=200; * number of imputations;
%let seed=314;

```

```

* obtain sample size in raw data;
proc sql noprint;
    select count(*) into :n from raw1;
quit;

data raw;
    set raw1(drop=subj);
    subj = _n_;
run;

options nonotes nosource;
ods noreresults;
ods html close;
ods graphics off;

data bootid;      * dummy data set to store bootstrapped subject numbers;
    seed=123;
    do boot=0 to 100;
        do i=1 to &n;
            if boot=0 then subj=i;
            else do;
                call ranuni(seed, u);
                subj=ceil(&n*u); * bootstrapped subject number;
            end;
            output;
        end;
    end;

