    call symput("seed", strip(put(seed,12.)));
    keep boot subj;
run;

* match the subject number to retrieve other subject-specific data;
proc sql noprint;
    create table bootsamp as
    select b.boot, a.subj, a.treated, a.followup, a.time, a.status a.complete a.episode
    from raw as a, bootid as b
    where a.subj=b.subj
    order by boot, subj;
quit;

* obtain posterior draws of model parameters from bootstrap samples;
proc phreg data=bootsamp;
    by boot;
    class episode region treated(ref='1');
    model time*status(0)=episode region treated;
    bayes nmc=%eval(&nimps*&thin) piecewise=hazard seed=314;
    ods output Partition=partition PosteriorSample=postsamp;
run;
ods output close;

* Boot samp data for both treatments
data bootsamp1;
set bootsamp;
if treated in (1,2); * Placebo Vs 1.5mg;
run;

data bootsamp2;
set bootsamp;
if treated in (1,3); * Placebo Vs 3.0;
if treated=3 then treated=2;
run;

/*Delta-Adjusted Method*/
%macro delta(postsamp=, bootsamp=, trt=, dataout=);

data postsam2;
    set &postsamp.;
    temp = (Iteration - 2000 - 1)/&thin + 1;
    _imputa_ = floor(temp);
    if _imputa_ = temp;
    rename &trt.=beta;
    keep boot _imputa_ lambda1-lambda&ninterval &trt.;
run;

```

```

*merge with raw data;
proc sql noprint;
    create table raw2 as
        select a.* , b.subj, b.treated, b.followup, b.time, b.status, b.complete, b.episode
        from postsam2 as a, &bootsamp. as b
        where a.boot=b.boot
        order by boot, _imputa_, subj;
quit;

* obtain maximum follow-up;
proc univariate data=&bootsamp. noprint;
    by boot;
    var time;
    output out=maxtime max=maxtime; * maximum survival time;
run;

* organize partition information;
proc transpose data=partitit out=partitit(drop=_name_ _label_)
    prefix=a;
    by boot;
    var UpperTime;
run;

data partitit;
    merge partitit maxtime;
    by boot;
    a&ninterval = maxtime+1; * a large number to represent infinity;
    drop maxtime;
run;

data raw2;
    merge raw2 partitit;
    by boot;
run;

* impute censored event times for early dropouts;
data raw4;
    set raw2 end=eof;
    if _n_=1 then seed=789;
    retain seed;

    array a{&ninterval};
    array lambda{&ninterval};

    call ranuni(seed, u);
    do delta=0 to 2 by 0.147;
    nlogu = -log(u)/exp(treated*(beta+delta)); * MNAR;

    * no imputation needed for subjects with events or for completers;
    if status=1 or (status=0 and time=followup) then do;
        time3 = time;
        status3 = status;

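### The primary and sensitivity programs in the SAP read the censoring flag CNSR with opposite meanings, so one of them counts non-relapsers as relapses

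*SAP*

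**What the plan says.** SAP Section 10.1 censors patients who do not meet a relapse criterion when they complete or leave the double-blind period, and refers to sample programs in Appendices I and II.

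**Appendix I (primary analysis).** The dataset is introduced with "Note in the dataset adtte (DB ITT population", and its indicator is defined in words: "cnsr is for the status of censored (=0) or relapsed (=1". The log-rank step uses "time aval * cnsr(0" and the Cox step uses "model aval * cnsr(0)= episode region trt02p/rl". In both, the value in brackets is the censored one, so the event is CNSR = 1. Text and code agree.

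**Appendix II (delta-adjusted and placebo-based analyses).** The program reads "ad.adtte(keep=aval cnsr paramn subjid trt03pn where=(paramn=0", and a comment says that this selects time to relapse. It then sets `status=(cnsr=0)`, so status is 1 when CNSR is 0. The model is "model time*status(0)=episode region treated", which makes status = 0 the censored value. The imputation step opens with the comment "no imputation needed for subjects with events or for completers" and the condition "if status=1 or (status=0 and time=followup) then do". Here the event is status = 1, that is CNSR = 0. The variable list in Appendix II labels CNSR only as a censoring variable and gives no values.

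**The concern.** A 0/1 indicator can be coded either way, but not both ways in one dataset. The documents do not show which coding the delivered dataset carries, and each possibility causes damage.

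- **The dataset follows Appendix I.** Appendix II then takes dropouts and completers as having relapsed on the day they left or finished, and takes true relapsers as censored. Because it imputes only patients with status = 0, no dropout is ever imputed. The delta and phi parameters, which exist to vary the assumed risk after dropout, would not touch the dropouts. The tipping point would have no meaning.
- **The dataset follows Appendix II.** The confirmatory log-rank test and hazard ratio then describe time to leaving the double-blind period without relapse, which is not the primary endpoint.

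**Working it through.** **1. The two codings side by side**

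| CNSR | Appendix I | Appendix II |
|---|---|---|
| 0 | censored | status = 1, event |
| 1 | relapse | status = 0, censored |

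They are exact opposites.

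**2. Expected relapses, to check against the plan's figure.** Inputs from SAP Section 14.0: 126 patients per arm, placebo relapse 35% at Week 39, HR 0.42, dropout 26%. I assume exponential relapse and dropout, with the same dropout hazard in every arm.

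- Cumulative hazards over 39 weeks: placebo relapse −ln(0.65) = 0.431; active relapse 0.42 × 0.431 = 0.181; dropout −ln(0.74) = 0.301.
- P(relapse observed) = [relapse / (relapse + dropout)] × [1 − exp(−(relapse + dropout))].
- Placebo: (0.431/0.732) × (1 − 0.481) = 0.305, and × 126 = 38.5.
- Each active arm: (0.181/0.482) × (1 − 0.618) = 0.144, and × 126 = 18.1.
- Total: 38.5 + 18.1 + 18.1 = 74.7, against about 75 in the SAP. The figure reproduces.

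One dose versus placebo has 38.5 + 18.1 = 56.6 events. Freedman power is Φ(√56.6 × 0.58/1.42 − 1.96) = 0.867, against the stated 85%. Schoenfeld's formula gives 0.904.

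**3. Patients misclassified under inversion.** 378 − 74.7 ≈ 303 non-relapsers become events and about 75 relapses become censored. For one dose versus placebo, 252 − 56.6 ≈ 195 false events replace 57 real ones.

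**4. Effect on a log-rank comparison.** Two-arm trials of 126 against 126, unstratified, 600 replicates:

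| Flag | Mean events | HR | Significant |
|---|---|---|---|
| Correct | 57 | 0.43 | 89% (benefit) |
| Inverted | 195 | 0.99 | 2.0% benefit, 1.3% harm |

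Larger runs agree. With the flag inverted, 1,500 two-arm trials gave a median HR of about 1.00 and 4.4% significant; 6,000 three-arm trials gave 1.01 and 4.8%. Correct-flag power was 89% in both.

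The null result has a simple cause. At Day 273 everyone still at risk becomes an event together, which adds nothing to the log-rank statistic. What remains compares dropout, and dropout was assumed equal across arms.

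This step covers a plain log-rank or Cox comparison. The further distortion from Appendix II's imputation was not simulated.

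**The case against.** The strongest reply is that these are sample programs and that Section 10.1 is clear in words about who is censored. A production program need not copy the flag. Appendix II as printed also looks unlikely to run: it assigns one library name and reads another, and it lists one treatment variable but keeps a differently numbered one. It also drops region before modelling it. Some of this may come from reading the PDF, but a programmer would have to rework the code anyway. Appendix I names its dataset without a library or parameter filter, so it could be a derived copy. Appendix II also tabulates events by treatment, and some 303 events in place of 75 would be hard to miss.

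Part of this stands. Harm requires the printed logic to be carried over to one dataset. The figures for an inverted primary test belong to the less supported branch, because the only written definition agrees with both Appendix I procedures. It is also uncertain whether true relapsers would be given imputed times. Section 7.1 counts relapsers as completing, and the code skips patients who completed with time equal to follow-up, yet a code comment puts relapsers in the other branch. Either way their relapse is lost as an event.

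The rest does not remove the conflict. Section 10.1 points to these programs, both use the same dataset name, and nothing recodes the variable. SAP Amendment #3 edited the appendix code to add region and left this in place. The event table has no expected count and is not tied to the primary analysis or to a relapse listing.

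**Conclusion.** The concern holds. The contradiction is in the printed code and needs no assumption. On the written definition, the error is the status line in Appendix II, and it would invalidate both planned checks on informative censoring. If the dataset is coded the other way, the primary test is inverted instead. The misclassification is about 303 false events and 75 lost relapses among 378 patients. An inverted primary comparison would fall from 89% power to about the 5% false-positive rate.

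The counts rest on the SAP's planning assumptions with exponential relapse and dropout. The near-null hazard ratio rests also on equal, noninformative dropout; with unequal dropout the inverted test would respond to that difference. This must be fixed, because it determines which patients count as events in the primary endpoint or in its sensitivity analyses.

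**What to change.** State one CNSR coding for the time-to-event dataset and use it throughout.

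- If 0 is censored and 1 is relapsed, as Appendix I says, change the Appendix II line to `status=(cnsr=1)`.
- If 0 is the event, correct the definition in Appendix I and use `aval*cnsr(1)` in both LIFETEST and PHREG.

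In either case, require the event count per arm to agree between the primary program, both sensitivity programs before imputation, and the relapse listing. The event table already in Appendix II can serve as the starting point.

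The coding change itself is a line or two of text and code, with no effect on conduct. Correcting the other slips in the printed Appendix II at the same time would take somewhat longer.

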The hypothesis testing will compare the time to relapse between each cariprazine group and placebo group using the log-rank test stratified by modified index episode (manic or depressive) and region (US, non-US) for the DB ITT population. To derive the modified index episode, the manic index episode(s) with or without mixed features will be classified as manic episode(s); depressive index episode(s) with or without mixed features will be classified as depressive episode(s). Estimates of the hazard ratio (HR) and 95% confidence intervals will be based on the Cox proportional hazards model with treatment group as the covariate stratified by modified index episode (manic or depressive) and region (US, non-US). The Kaplan-Meier estimates for the cumulative distribution of the relapse rate for each treatment group will be provided.

Per the protocol, relapses are collected within a double-blind treatment period that lasts with a maximum of 39 weeks (or 273 days + 3 days visit time window), hence all survival analyses will censor data at 276 days.

The primary hypotheses for cariprazine 3.0 mg/d and 1.5 mg/d treatment groups versus placebo will be tested sequentially in order to control the overall Type I error rate. The comparison of cariprazine 3.0 mg/d versus placebo will be tested first at two-sided 0.05 significance level, and only when it is significant, the comparison of cariprazine 1.5 mg/d versus placebo will be tested also at the two-sided 0.05 significance level. This testing strategy controls the overall Type I error rate at 0.05 significance level.

Two sensitivity analyses will be performed to assess the robustness of the primary analysis results to the possible violation of the noninformative censoring assumption.

The first sensitivity analysis will be based on the delta-adjusted method examined by Zhao et al. (2014), which specifies that the hazard of having an event for subjects who discontinued before the time point is increased relative to the hazard for subjects who continued beyond the time point for the experimental treatment group. The delta-adjustment will be gradually increased from zero until reaching the tipping point when the statistical significance of the primary efficacy endpoint is overturned, and the plausibility of the magnitude of delta-adjustment needed for reaching the tipping point will be subject to clinical scrutiny.

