14.0 DETERMINATION OF SAMPLE SIZE

The sample size and power calculations are based on the analysis of time to relapse of any mood episode in the DBTP to compare each cariprazine dose group versus placebo-based on a log-rank test. The trial will be a fixed follow-up design. Patients are followed from randomization until dropout, relapse or a fixed duration of 39 weeks.

The relapse HR is assumed to be 0.42 based on cariprazine maintenance study in patients with schizophrenia ([Durgam 2016](#)) [REDACTED] compounds (asenapine and aripiprazole) in bipolar I disorder trials and schizophrenia maintenance trials were similar ([Pigott 2003; Keck 2006; Kane 2011; Szegedi 2018](#)). The cumulative relapse rate at Week 39 for the placebo group is assumed to be 35%, which is the average of the relapse rate in the placebo arm at Week 39 for the asenapine bipolar mania maintenance trial ([Kane 2011](#)) and the quetiapine bipolar I disorder maintenance trial ([Suppes 2009](#)).

Using these assumptions, the study would have to observe approximately 75 events to have 85% statistical power to detect that at least 1 dose is significant. The statistical method for the power calculation is based on the log-rank 2-sided test at the 5% significance level to compare the difference of each of the 2 survival curves of the cariprazine treatment groups versus that of placebo. Based on the assumed event rates, and considering the 26% of patients who may discontinue early from the study due to other reasons, approximately a total of 378 patients should be randomized to cariprazine 3.0 mg/d, cariprazine 1.5 mg/d, and placebo, or approximately 126 patients per treatment group.

It should be noted that this study is designed to test the 3.0 mg/d dose of cariprazine versus placebo first at the 0.05 significance level and, if the results are significant, then the 1.5 mg/d dose of cariprazine will be tested at the 0.05 significance level. Given this sequential testing strategy, the higher dose of 3.0 mg/d has 85% statistical power to show significance versus placebo, and the 1.5 mg/d dose, if it is as effective as the 3.0 mg/d dose, and the 3.0 mg/d dose is statistically significant, would also have 85% statistical power at the 0.05 significance level.

With the expectation that approximately 46% of patients will complete the OLTP period and will meet the randomization criteria, approximately 882 patients would be expected to enter and be treated with cariprazine in the OLTP.

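### Appendix I's sample log-rank code takes in all three arms: run literally, each dose's p-value depends on the other dose, and 5% control can be lost when only one dose works

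*SAP*

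**What the plan says.** SAP 10.1 describes the primary test as one that will "compare the time to relapse between each cariprazine group and placebo group using the log-rank test", stratified by modified index episode and region. On order and level it says: "The comparison of cariprazine 3.0 mg/d versus placebo will be tested first at two-sided 0.05 significance level"; 1.5 mg is tested at the same level only if that succeeds. It concludes: "This testing strategy controls the overall Type I error rate at 0.05 significance level". SAP 14.0 bases power on the same pairwise view, a log-rank test to "compare the difference of each of the 2 survival curves of the cariprazine treatment groups versus that of placebo".

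SAP Appendix I gives the sample program. Its header reads "SAS program for log-rank test comparing treatment groups trt02pn=0 and =1", which is two groups. The step below it begins "proc lifetest data=adtte method=km", with adtte described as the double-blind ITT population, and then requests "strata episode region/test=logrank group=trt02p diff=control('Placebo". There is no WHERE clause, BY step or earlier subset. The Cox step that follows reads the same data set and has contrasts for both doses, so adtte holds all three arms.

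In SAP Appendix II the two-arm subset is written out: "if treated in (1,2); * Placebo Vs 1.5mg", with a matching step for 3.0 mg.

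**The concern.** With three groups and a control-difference request, the procedure computes one vector of observed minus expected events and one covariance matrix over all three arms. Each dose is then compared with placebo by a contrast within that system. Expected events and variance for 3.0 mg against placebo therefore depend partly on how often the 1.5 mg arm relapses, and the reverse.

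A fixed sequence protects the familywise error in every configuration only if each test keeps its 5% size whatever the other dose does. A two-arm log-rank does. The three-arm contrast does so only when the third arm's hazard matches that of the two being compared. If the third arm relapses less, the pooled variance is too small and the test rejects too often.

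A full dose that works and a reduced dose that does not is a result this dose-reduction design has to be able to detect. Text and code also point to two different primary p-values, so the confirmatory test is not uniquely fixed in advance.

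**Working it through.** **Inputs.** From SAP 14.0: HR 0.42, placebo relapse 35% at Week 39, 26% discontinuation for other reasons, 39 weeks of fixed follow-up, 126 per arm, about 75 events, 85% power. From SAP 10.1: two-sided 0.05, 3.0 mg first, strata of episode and region (2 × 2 = 4).

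**The plan's own figures.**
- Schoenfeld events per pair: 4(1.960 + 1.036)² / (ln 0.42)² = 47.7, i.e. 48.
- Relapse on cariprazine: 1 − 0.65^0.42 = 16.55%.
- Patients per arm: 48 / (0.35 + 0.1655) / 0.74 = 125.8, i.e. 126.
- Three-arm events with exponential relapse and dropout: 126 × (0.3055 + 2 × 0.1436) = 74.7, i.e. 75.

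The sample size and event count therefore reproduce, with a pairwise comparison as the basis. The two use different dropout models (simple attrition for patients, exponential dropout for events), which does not affect this point.

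**Analytic check.** Take equal risk sets of n per arm and placebo hazard λ. One dose has no effect and the other has HR h. The total event rate is (2 + h)nλ.
- Variance used by the three-arm contrast: (2/9 + 2/9 + 2/9)(2 + h)nλ = (2/3)(2 + h)nλ. At h = 0.42 this is 1.61nλ.
- True variance of the difference in events between the null dose and placebo: 2.00nλ.
- Effective critical value: 1.96 × √(1.61/2.00) = 1.76, a two-sided error of about 7.8%.

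This ignores how the risk sets change as patients relapse, and it somewhat overstates the simulated error.

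**Simulation.** There were 20,000 trials per scenario (Monte Carlo SE about 0.15 to 0.19 points for error rates). Assumptions: exponential relapse and dropout, continuous event times, four strata holding an assumed 30/20/30/20% of patients, and the same hazard in each stratum. Three-arm contrast: z = (U_dose − U_plc) / √(V_dd + V_pp − 2V_dp), from one stratified three-arm log-rank. Comparator: the stratified two-arm log-rank on the same data.

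| HR 3.0 / HR 1.5 | Quantity | Three-arm contrast | Two-arm test |
|---|---|---|---|
| 1 / 1 | Error of first test (3.0 mg) | 5.05% | 5.0% |
| 1 / 0.42 | Error of first test (3.0 mg) | 7.2% | 5.2% |
| 0.42 / 1 | Error of 1.5 mg test taken alone | 7.05% | 5.1% |
| 0.42 / 1 | Error of 1.5 mg test in sequence | 4.95% | 3.8% |
| 0.42 / 1, placebo rate 50% (assumed) | Error of 1.5 mg test in sequence | 5.7% | 4.7% |
| 0.20 (assumed) / 1 | Error of 1.5 mg test in sequence | 7.6% | 4.8% |
| 0.42 / 0.42 | Power, 3.0 mg and 1.5 mg | 90.4%, 90.3% | 88.3%, 88.0% |
| 0.42 / 1 | Power, 3.0 mg | 86.1% | 88.1% |

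In the first two rows the first test's error is also the familywise error, because 1.5 mg cannot be declared unless 3.0 mg is.

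Separate runs of 8,000 to 12,000 trials put the second row at 6.7% to 7.25%, against 4.8% to 5.2% two-arm. With 3.0 mg at an assumed HR of 0.30 and 1.5 mg null, the 1.5 mg error in sequence was 6.9% to 7.1%, against 4.8% to 5.0%.

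The two methods gave different decisions on a given dose in about 0.1% to 5% of trials, depending on the scenario.

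**The case against.** The strongest reply is that the specified method is sound and the fault lies only in code that the SAP itself calls a sample. SAP 10.1 describes pairwise tests, which are valid in sequence, and the Appendix I header names two groups. If the data were first cut to two arms, the same STRATA line would give the ordinary two-arm test and the problem would disappear. All of that stands. But no such cut is written, the header does not say which dose is meant, and the Cox step needs both doses in the same data set. SAP 10.1 refers the reader to Appendix I for the primary analysis, and SAP Amendment #3 revised the appendix code to add region.

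Second, how control differences are computed is a property of the software and appears nowhere in the documents. That also stands, and the finding is conditional on it.

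Third, Appendix II is imperfect evidence of a two-arm intent. Its imputation model is fitted to all arms before the split, and only the later tests are two-arm.

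A reader might infer that pooling is why the Appendix II results at delta = 0 or phi = 0 would not reproduce the primary p-value. The documents do not support that. At those settings the program still imputes event times for early dropouts and combines 200 imputations, so a two-arm primary test would not match either.

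**Conclusion.** The Appendix I code does not match SAP 10.1 or its own header. Run literally, and assuming pooled three-arm control differences, it loses strong 5% control when one dose is null and the other is effective. The error is about 7% instead of 5%:
- for the first test, if 3.0 mg is null and 1.5 mg has HR 0.42;
- for 1.5 mg in sequence, if 1.5 mg is null and 3.0 mg is stronger than planned (HR 0.30, which is our assumption).

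A reader might go further and conclude that the trial's Type I error control simply fails. The documents do not support that. The SAP 10.1 procedure is valid as described. Even the literal code holds 5% if neither dose works. It also stays at about 5% in sequence if 3.0 mg has HR 0.42 and 1.5 mg has no effect, although only because 3.0 mg then misses significance in about 14% of trials; the 1.5 mg test itself runs at about 7%. The excess is about 2 percentage points, two-sided.

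This should be fixed before unblinding. The pooled version has slightly more power when both doses work, so a choice between the two made after unblinding would be open to challenge.

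**What to change.** In Appendix I, run the stratified log-rank twice, each time with a WHERE clause: once on placebo and 3.0 mg, once on placebo and 1.5 mg. Keep the strata of episode and region and the treatment group variable; the control-difference request is then unnecessary. Correct the header to name the arms in each run. Add a sentence to SAP 10.1 that each log-rank test uses only the two arms compared. Apply the same rule to the other log-rank analyses: the subgroups, time to early discontinuation, and the Russia/Ukraine sensitivity analysis.

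The cost is a small SAP and code edit. There are two statistical downsides. Power is slightly lower if both doses work (about 88% against 90% per dose), although it is higher for 3.0 mg if only that dose works (88.1% against 86.1%). And if the Cox model stays three-arm, the hazard ratio and its interval will not come from exactly the same data as the p-value; the SAP should say so.
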